Study objectives	
The primary objective:
 
- Evaluate efficacy of ibrutinib + venetoclax (VI) in terms of proportion of patients fulfilling the criteria for progression free survival (PFS) at 12 months after stopping therapy (27 months after starting treatment) for patients randomized to stop treatment (arm B of the study), reinitiated treatment due to MRD positivity not considered progression (see section 13.1 for details). 
Secondary objectives (for all treatment groups):
 
- Evaluation of the efficacy in terms of minimal residual disease (MRD) at 12 months after stopping treatment (month 27),- Evaluation of efficacy in terms of PFS (IWCLL criteria),- Time to next CLL treatment,- MRD after cycle 12 (PB), at day 15 of cycle 15 (PB and BM) and at later time points in PB,- Overall Survival (OS),- Complete response (CR)/ Partial Response (PR)/ Stable disease (SD) after cycle 3, 9, 12, 15, and at month 27 and month 51 (3 years after stopping treatment),- Duration of response,- To evaluate safety with regards to type, frequency, and severity of adverse events (AEs) and adverse events of special interest (AESI) and their relationship to study

treatment,

- To evaluate patient related outcomes, measured in terms of health-related quality of life (QoL) by EORTC QLQ-C30 and QLQ-CLL16 questionnaires.

Secondary objectives (Arm B group)

- Time to and number of patients reinitiating treatment,
- Time to treatment failure after reinitiated treatment.

Study design

Phase-II trial, prospective, multicenter, open-label, randomized.

Patient population

Fit (CIRS \leq 6) and unfit (CIRS $>$ 6) patients with a creatinine clearance \geq 30 ml/min with previously treated CLL with or without TP53 aberrations requiring treatment.

Intervention

All patients receive ibrutinib + venetoclax (with delayed start and ramp up of venetoclax from cycle 3) for the 15 cycles. Patients not achieving MRD negativity after cycle 12 (PB) AND/OR day 15 cycle 15 (PB+BM) continue on ibrutinib maintenance (non-randomized group). Patients achieving MRD negativity after cycle 12 (PB) AND day 15 cycle 15 (PB+BM) are randomized 1:2 between ibrutinib maintenance (arm A) and stopping treatment (observation, arm B).

Patients randomized to arm B who become MRD positive or have symptomatic CLL according to IWCLL criteria during the observation period reinitiate treatment with both ibrutinib and venetoclax for 12 cycles and continue ibrutinib treatment until toxicity or progression.

Only patients randomized for observation (arm B) are considered for the primary endpoint without formal comparison between arms.

Duration of treatment

All patients receive ibrutinib + venetoclax (with delayed start

and ramp up of venetoclax from cycle 3) for the first 15 cycles.

Thereafter Ibrutinib maintenance until progression/toxicity or observation without treatment.

Patients randomized to arm B who become MRD positive or have symptomatic CLL according to IWCLL criteria during the observation period reinitiate treatment ibrutinib + venetoclax for 12 months and continue ibrutinib treatment until toxicity or progression.

Subsequently all patients will be followed until 7 years after registration

Target number of patients	207 eligible patients. In order to take into account possible dropout due to ineligibility, 230 patients will be registered
Expected duration of accrual	Expected start of recruitment Q2/2017 Expected end of recruitment Q2/2020
Main study endpoints	
Primary endpoints: (Only considered for arm B of the study)
 
 - Proportion of patients fulfilling the criteria for progression free survival (PFS) at 12 months after stopping therapy (27 months after starting treatment) for patients randomized to stop treatment , reinitiated treatment due to MRD positivity not considered progression (see section 13.1 for details). 
Secondary endpoints (for all treatment groups):
 
 - Minimal residual disease (MRD) at 12 months after stopping treatment (month 27) for patients randomized to stop treatment, - PFS (IWCLL criteria), - Time to and number of patients reinitiating treatment, - Time to treatment failure after reinitiated treatment, - Time to next CLL treatment, - MRD after cycle 12 (PB), day 15 cycle 15 (PB and

- BM) and at later time points in PB,
- Overall survival (OS),
- Complete response (CR)/ Partial Response (PR)/ Stable disease (SD) after cycle 3, 9, 12, 15 and month 27 and 51 (3 years after stopping treatment),
- Duration of response,
- Safety parameters: Type, frequency, and severity of
 - o adverse events (AEs) and
 - o adverse events of special interest (AESI) and their relationship to study treatment
- Health-related quality of life by EORTC QLQ-C30 and QLQ-CLL16 questionnaires.

Exploratory endpoints:

- Evaluation of relationship between various baseline markers and clinical outcome parameters,
- Various markers at time of progression,
- Correlation between MRD in BM and PB,
- Correlation between MRD in BM and PFS//OS,
- Correlation between MRD in PB and PFS/OS.

Benefit and nature and extent of the burden and risks associated with participation

The standard of care in treatment of patients with relapsed or refractory CLL (RR CLL) is rapidly changing. For patients with a relapse later than 1-2 years from first line therapy, repeated therapy with a first line regimen is used. This poses the risk of significant immunosuppression and infectious complications as well as a shorter progression free survival than for first line treatment is expected. For patients with refractory disease, early relapse or emerging of TP53 aberrated subclones, targeted treatment with ibrutinib or idelalisib + rituximab is used. However, literature to date only supports treatment until progression or toxicity with significant impact on quality of life and significant socioeconomic implications as well as conferring the risk of clonal evolution and development of resistance with continuous exposure to treatment.

Thus, there is an urgent need for alternatives, especially

chemotherapy-free regimens without the need for prolonged maintenance.

As CD20 targeting agents are currently part of standard first line treatment for CLL, testing of a regimen for RR CLL without repeated CD20 targeting, thus presenting targets for treatment that have not been targeted previously for the patients, is a rational approach.

Ibrutinib is approved for treatment of patients with CLL as first line treatment and for patients with relapsed or refractory disease with a manageable safety profile.

Venetoclax has been approved for treatment of patients with CLL and del(17p), with a manageable safety profile as long as precautions concerning the risk of tumor lysis syndrome are followed as stated for this trial. Several hundreds of patients have been treated with the combination of ibrutinib and venetoclax in clinical trials, no unexpected safety signals differing from the safety profile described for each drug have been reported. However, data on long term safety and the outcome upon stopping treatment is still immature, thus the current study especially addresses these aspects in addition to the primary endpoint.

Consequently, the aim of the current trial is to evaluate if combination treatment with venetoclax + ibrutinib in patients with RR CLL can lead to MRD negativity, which may induce long lasting remissions for those patients randomized for observation after cycle 15.

Planned interim analysis and DSMB

The interim analyses of the trial are described in section 14.4.4.

Real time monitoring of the outcome for patients randomized for stopping treatment will continue based on the MRD results. MRD data will be collected at the 2 central laboratories and shared with central data management.

4 Investigators and study administrative structure

Responsibility	Name	Affiliation/Address
Sponsor	HOVON	VU University Medical Center, [name] The Netherlands [contact]
Co-sponsor	NCLLSG	Rigshospitalet, Copenhagen University Hospital Department of Hematology, Building 4042 [name] Denmark [contact]
Representative of Sponsor (HOVON)	[name], chairman [name], treasurer	Erasmus MC, Rotterdam Radboud University, Nijmegen
Principal Investigator	[name]	Copenhagen University hospital, Rigshospitalet Department of Hematology, building 4042 [name] , Denmark [contact] Mail: [contact]
	[name]	Academic Medical Center University of Amsterdam Department of Hematology F4-224 [name], The Netherlands [contact] Mail: [contact]
Co-investigators	[name]	Albert Schweitzer hospital Department of Internal Medicine [name], The Netherlands [contact] Mail: [contact]
	[name]	Uppsala University Hospital [name], Sweden [contact] Mail: [contact]

Coordinating investigator	The Netherlands	
	[name]	Academic Medical Center, Amsterdam
	Denmark	

5.1 Description of disease and current treatment

Chronic lymphocytic leukemia (CLL) is the most common leukemia in adults. CLL is characterized by clonal proliferation and accumulation of neoplastic B-cells within the blood, bone marrow and secondary lymphatic organs (Chiorazzi, Hatzi et al. 2005). The B-cell receptor (BCR) pathway has in recent years been at the core for development of new therapeutics for patients with CLL. High efficacy of novel kinase inhibitors (the of Brutons Tyrosine Kinase (BTK) inhibitor ibrutinib and the PI3K inhibitor idelalisib) targeting the BCR pathway led to approval for patients with relapsed/refractory CLL, including first line treatment of CLL patients with del(17p) or TP53 mutations (Byrd, Furman et al. 2013, Furman, Sharman et al. 2014, Farooqui, Valdez et al. 2015). Besides the significance of the BCR pathway, CLL cells show resistance to apoptosis due to upregulation of the anti-apoptotic protein Bcl-2, which can be inhibited in the clinical setting with the Bcl-2 inhibitor venetoclax, recently approved for clinical use by the FDA (Roberts, Davids et al. 2016).

The standard of care in treatment of patients with relapsed or refractory CLL (RR CLL) is rapidly changing. For patients with a relapse later than 2 years from first line therapy, repeated therapy with a first line regimen is used. This poses the risk of significant immunosuppression and infectious complications as well as a shorter event free survival than for first line treatment is expected. For patients with refractory disease, early relapse or emerging TP53 aberrated subclones, targeted treatment with ibrutinib, idelalisib + rituximab or venetoclax is used. However, published studies to date only supports treatment until progression or toxicity with significant impact on quality of life and significant socioeconomic implications. Thus, there is an urgent need for alternatives, especially chemotherapy-free regimens without the need for prolonged maintenance in the setting of RR CLL.

5.2 Investigational Medicinal Products

5.2.1 Venetoclax

Venetoclax is an oral bcl-2-antagonist, which in contrast to ABT-263 is specific for bcl-2 and induces death in bcl-2 dependent tumor cells while sparing thrombocytes (Souers, Levenson et al. 2013, Ng and Davids 2014). Venetoclax was shown to be potent in cell-killing and anti-tumor effects, but also enhanced the efficacy of drugs like bendamustine and rituximab in xenograft mouse models. It is co-developed for the treatment of hematological and immunological diseases by the pharmaceutical companies F. Hoffmann-La Roche LTD and AbbVie Inc. Venetoclax has been approved for treatment of CLL by the FDA in April 2016. Concerning detailed information on Venetoclax please refer to the current version of the IB.

Venetoclax is currently investigated in trials including patients with relapsed/refractory CLL/ small lymphocytic lymphoma (SLL), that were heavily pretreated and harbor adverse prognostic features, such as del(17p) and unmutated IGHV status. In the first-in-human trial even a single dosage lead to a rapid reduction of tumor burden. However, the overwhelming and rapid dying of malignant cells caused severe and sometimes even fatal tumor lysis syndromes (TLS), which could be managed or even prevented with certain measures of precaution, especially during the first days of treatment and during the dose-escalation phase. Thus, the target dose of 400 mg venetoclax per day has been kept in ongoing trials without significant safety findings concerning tumor lysis syndrome, as long as the careful dose-escalation also implicated in the current study is followed.

Aside from these TLS, venetoclax was found to be safe and well tolerated. Preliminary results from trials evaluating venetoclax as a monotherapy and combined with rituximab were very encouraging: an overall response rate of 79% and CR rate of 34% and even some cases of minimal residual disease (MRD) negativity were achieved with single agent venetoclax, however, these results appeared to be independent of adverse factors such as IGHV and cytogenetics as well as refractoriness to fludarabine (Roberts, Davids et al. 2016). In an ongoing dose-escalation study, the combination of venetoclax and rituximab showed no additional toxicities, of note, no further TLS occurred after dosing and monitoring was changed due to one fatal hyperkalemia due to TLS. (Roberts, Ma et al. 2015) An overall response rate of 88% and a CR/CRi rate of 31% were achieved. Of 15 patients with CR/CRi and 22 patients with PR 17 were MRD-negative in the bone marrow.

5.2.2 Ibrutinib

Ibrutinib is an oral, first-in-class selective, irreversible small molecular inhibitor of Bruton's Tyrosine Kinase (BTK) currently under development in B-cell malignancies. Ibrutinib is being co-developed by Pharma-cyclics, Inc. and Janssen Research & Development, LLC (JRD). Ibrutinib was approved by the FDA in February 2014 and by the EMA in October 2014 for the treatment of CLL patients who have received at least one previous therapy and also for patients with del(17p) or TP53 mutations. For detailed in-formation on ibrutinib please see the current version of the investigator's brochure and the SmPC.

Ibrutinib showed excellent responses and a safe toxicity profile and therefore warrants to be implemented into clinical trials (Byrd, Furman et al. 2013).

5.3 Rationale of the study

Preclinical data supports the combination of the BTK inhibitor ibrutinib and the bcl-2 inhibitor venetoclax. The combination of ibrutinib and venetoclax showed synergy in a diffuse large B cell lymphoma (DLBCL) cell line model (Mathews Griner, Guha et al. 2014) and in primary CLL cells

(Deng, Isik et al. 2015) as well as in Mantle Cell Lymphoma (MCL) cell lines.(Portell, Axelrod et al. 2014) CD20 targeting agents are currently part of standard first line treatment for CLL. Testing of a regimen for RR CLL without repeated CD20 targeting, thus presenting targets for treatment that has not been targeted previously for these patients, is a rational approach. Furthermore, several clinical trials are currently testing the combination of venetoclax and ibrutinib for clinical use, with no unexpected toxicities reported so far through scientific meetings, publications or internal reports for the marketing holders. Consequently, the aim of the current trial is to evaluate if combination treatment with venetoclax + ibrutinib in patients with RR CLL can lead to MRD negativity, which may induce long lasting remissions.

6 Study objectives

The primary objective:

- Evaluate efficacy of ibrutinib + venetoclax (VI) in terms of proportion of patients fulfilling the criteria for progression free survival (PFS) at 12 months after stopping therapy (27 months after starting treatment) for patients randomized to stop treatment (arm B of the study), reinitiated treatment due to MRD positivity not considered progression (see section 13.1 for details).

Secondary objectives (for all treatment groups):

- Evaluation of the efficacy in terms of minimal residual disease (MRD) at 12 months after stopping treatment (month 27),
- Evaluation of efficacy in terms of PFS (IWCLL criteria),
-
- Time to next CLL treatment,
- MRD after cycle 12 (PB), day 15 cycle of 15 (PB and BM) and at later time points in PB,
- Overall Survival (OS),
- Complete response (CR)/Partial response (PR)/Stable disease (SD) after cycle 3, 9, 12, 15, and at month 27 and month 51 (3 years after stopping treatment),
- Duration of response,
- To evaluate safety with regards to type, frequency, and severity of adverse events (AEs) and adverse events of special interest (AESI) and their relationship to study treatment,
- To evaluate patient related outcomes, measured in terms of health-related quality of life (QoL) by EORTC QLQ-C30 and QLQ-CLL16 questionnaires.

Secondary objectives (Arm B group)

- Time to and number of patients reinitiating treatment,
- Time to treatment failure after reinitiated treatment.

7 Study design

This study is designed as a phase 2 study with a late randomization in patients MRD negative after cycle 12 and 15, no formal comparisons between the two randomized treatment arms will be made.

During the treatment period all patients receive 15 cycles (28 days each) of oral ibrutinib + venetoclax treatment. During the first 2 cycles, only ibrutinib 420 mg a day is administered. From day 1 in cycle 3, ramp up over five weeks of venetoclax from 20 mg per day to the target of 400 mg per day is administered.

Patients achieving MRD negativity after cycle 12 in peripheral blood (PB) and at day 15 of cycle 15 in PB and bone marrow (BM) are randomized 1:2 between continuous ibrutinib treatment until toxicity or progression (arm A) and treatment free observation (arm B). Patients not reaching MRD negativity after cycle 12 and/or at day 15 of cycle 15 continue ibrutinib treatment until toxicity or progression (non-randomized patients).

MRD negative patients will be closely monitored for relapse/progression during the first 3 years after randomization by means of rapid reporting as described in section 16.1.1.

Patients becoming MRD positive (defined as $MRD \geq 10^{-3}$ and at least one month later $MRD \geq 10^{-2}$), or have symptomatic CLL according to IWCLL criteria (appendix A) during the observation period reinitiate treatment with both ibrutinib and venetoclax for 12 cycles and continue ibrutinib treatment until toxicity or progression.

Patients failing on reinitiating therapy (not reaching any response (CR/PR/SD) according to IWCLL criteria as assessed by the local investigator after 3 cycles of reinitiated therapy (or after reinitiation therapy until 12 months after randomization if progression occurred within 9 months from randomization) are considered as having progressive disease and will go off protocol treatment.

Details of all treatments (dose and schedule) are given in section 9.

8 Study population

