9.4 Reinitiation of therapy for patients randomized to arm B

Patients randomized to Arm B will get reinitiation of therapy during the observation period in case of:

- progression according to IWCLL criteria or
- $MRD \geq 10^{-3}$ (PB) and at least one month later $MRD \geq 10^{-2}$ (PB).

Treatment reinitiation will be as follows:

Venetoclax ramp up as outlined below for cycle 1, day 1 until day 28 after reinitiation, thereafter 400 mg daily (4 tablets. at 100 mg) until 12 cycles of 28 days (from reinitiation of ibrutinib).

Ibrutinib will be administered as a daily oral dosage of 420 mg (3 x 140mg) starting on day 1 of cycle 1 until:

- 1.) Progressive disease (patients not reaching any response (CR/PR/SD) according to IWCLL criteria as assessed by the local investigator after 3 cycles of reinitiated therapy are considered as progressive disease and will go off protocol treatment)

or

- 2.) unacceptable toxicity, whatever occurs first

The continuous daily administration with a slow dose escalation of venetoclax starts on cycle 1 day 1.

Agent	Dose/day	Route of administration	Cycle	Days
Ibrutinib	420 mg	Orally	1-until progression	1-28
Venetoclax	20 mg	Orally	1	1-7
Venetoclax	50 mg	Orally	1	8-14
Venetoclax	100 mg	Orally	1	15-21
Venetoclax	200 mg	Orally	1	22-28
Venetoclax	400 mg	Orally	2-12	1-28

The same precautions regarding TLS are to be taken as described in section 9.2.1.

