11.1 Withdrawal of individual patients from protocol treatment

Patients should be withdrawn from protocol treatment if any of the following criteria for withdrawal are met:

- ◆ Death

- ◆ Progressive disease after cycle 6 of induction treatment
In case of suspected progressive disease according to IWCLL at or after start of cycle 6, response assessment will be performed and only patients with at least SD will continue on trial; patients with progressive disease will go off protocol treatment.
In the case of signs of progression before start of cycle 6 i.e. Richter's, the local investigator must make a full diagnostic work up to assess whether the patient should go off protocol treatment due to progression.
- ◆ Progressive disease after at least 3 cycles of reinitiation treatment
- ◆ If, for whatever reason, one or both drugs are not given for more than 56 consecutive days
- ◆ If the patient receives systemic treatment for another malignancy during the protocol treatment

Patients can leave the study at any time for any reason if they wish to do so without any consequences. The investigator can also decide to withdraw a patient from protocol treatment for other reasons than the criteria described above. Examples of such reasons for withdrawal from protocol treatment are:

- ◆ Excessive toxicity
- ◆ Refusal of patient to continue protocol treatment
- ◆ No compliance of the patient: patient is unable or unwilling to adhere to the treatment schedule and/or procedures required by the protocol

Patients who are withdrawn from protocol treatment will receive medical care according to local practice.

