- cervical (head and neck, including Waldeyers ring, involvement of more than one group of nodes counts as one area)
- axillary (involvement of both axillae counts as one area)
- inguinal lymphadenopathy (including superficial femorals, involvement of both groins counts as one area)
- splenomegaly
- hepatomegaly

B. Response criteria

(Halek et al, 2008)

Response assessment will be based on the revised guidelines of the international workshop on CLL (IWCLL); these are as follows (see table on the next page) – a separate manual will be supplied to indicate the exact response assessment guidelines.

Complete remission (CR)¹ :

All below listed criteria must be fulfilled and no disease related symptoms should be present.

Complete remission with incomplete recovery of the bone marrow (CRi)¹:

All below listed criteria must be fulfilled, except for an incomplete recovery of the bone marrow with persisting anemia, thrombocytopenia and/or neutropenia (related to toxicity of treatment and not due to CLL) and no disease related symptoms should be present.

Partial response (PR):

Among the below listed criteria at least 2 from group A and 1 from group B must be fulfilled.

PR lymphocytosis:

PR without a 50% decrease in blood lymphocytes

Stable disease (SD):

Failure to achieve a PR and absence of PD.

Progressive disease (PD):

Presence of at least 1 of the below enlisted criteria or appearance of new lymph nodes >1.5cm, hepato- or splenomegaly or organ infiltration by CLL.

Relapse:

progressive disease more than 6 months after PR/CR was reached.

¹ A clinical CR/CRi fulfills the same criteria as a CR or CRi but was not (yet) confirmed with a bone marrow examination.

Parameter	CR	Cri	PR	PD
Group A (indicating tumor load)				
Lymphadenopathy ¹	none >1.5cm		decrease ≥50%	increase by ≥50% or new lymph nodes ≥1.5cm
Hepatomegaly	None		decrease ≥50%	increase by ≥50%
Splenomegaly	None		decrease ≥50%	increase by ≥50%
Blood lymphocytes	<4000/μl		decrease of ≥50% from baseline	increase by ≥50% over baseline to ≥5000/μl
Bone marrow	normocellular	hypocellular	50% reduction in BM infiltrates ²	irrelevant
	<30% lymphocytes, no B-lymphoid nodules			
Group B (indicating function of the hematopoietic system)				
Platelet count	≥100000/μl	Irrelevant	≥100000/μl or increase by ≥50% from baseline	decrease by ≥50% due to CLL
Hemoglobin	>11g/dl (6.8 mmol/L)	Irrelevant	>11g/dl or increase by ≥50% from baseline	decrease by > 2g/dl (1.2 mmol/L)

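### Protocol sections 7 and 9.4 give different times for taking an arm B patient off restarted treatment when progression came within 9 months and there is no response; section 11.1 does not settle it

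*Protocol*

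**What the plan says.** Section 7 (Study design) defines failure on restarted therapy as no CR, PR or SD, "as assessed by the local investigator after 3 cycles of reinitiated therapy". A parenthesis then gives a second time point for early progressors: "or after reinitiation therapy until 12 months after randomization if progression occurred within 9 months from randomization". One consequence closes the sentence and attaches to both time points: these patients "are considered as having progressive disease and will go off protocol treatment".

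Section 9.4 (Reinitiation of therapy) repeats the rule with the same response categories but without the parenthesis. Patients with no response "after 3 cycles of reinitiated therapy are considered as progressive disease and will go off protocol treatment".

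Section 11.1 opens with "Patients should be withdrawn from protocol treatment if any of the following criteria for withdrawal are met" and lists "Progressive disease after at least 3 cycles of reinitiation treatment" among the criteria. It makes no exception for early progression.

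Appendix B defines stable disease as "Failure to achieve a PR and absence of PD". Section 9.4 sets the cycle length on restart: "until 12 cycles of 28 days (from reinitiation of ibrutinib").

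**The concern.** The failure rule tells a site when to take a patient off two drugs. For one group of arm B patients, section 7 puts that time at 12 months after randomization and section 9.4 puts it at the end of cycle 3. Two sites that each follow the protocol could therefore treat the same non-responding patient differently.

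The page followed also decides whether a late response can still occur on protocol treatment. Section 13.1 counts a response obtained up to 12 months after randomization. Under section 9.4 an early progressor without a response at cycle 3 has already left treatment. In addition, the date of the secondary endpoint on time to treatment failure after restart could depend on the section used, if its event is leaving treatment for failure.

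**Working it through.** **1. Who is affected.** SD counts as a response in sections 7 and 9.4. By Appendix B, SD is the absence of both PR and PD, so an assessed patient with none of CR, PR or SD has PD. The patients concerned are those in arm B who progress clinically within 9 months of randomization, restart, and have PD on restarted treatment.

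**2. The passages side by side, for such a patient at the end of cycle 3.**

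| Section | Status at end of cycle 3 |
|---|---|
| 7, with its exception | Not yet a failure; assessed at 12 months after randomization |
| 9.4 | Failure; off protocol treatment |
| 11.1 | PD after at least 3 cycles; withdrawal criterion met |

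Section 11.1 sets a minimum, so the direct conflict is between sections 7 and 9.4. Section 11.1 still gives the extension no support, because PD at the end of cycle 3 already meets its criterion.

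**3. Where there is no conflict.** For progression after 9 months, section 7 falls back on 3 cycles, which agrees with 9.4 and 11.1. The exception is worded for progression, so it does not clearly reach patients who restart for MRD positivity.

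**4. Size of the gap.** The plan gives no figure of its own here. Inputs are the 28-day cycle (section 9.4) and the 3-cycle, 9-month and 12-month limits (sections 7 and 9.4). Restart on the day of progression is an assumption.

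- Month length: 365.25 / 12 = 30.4375 days.
- 3 cycles: 3 × 28 = 84 days; 84 / 30.4375 = 2.76 months.
- Exit under 9.4 for progression at month t: t + 2.76.
- Exit under section 7 for t within 9 months: 12.
- Gap in days: (12 − t) × 30.4375 − 84.

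| Progression (month) | Exit under 9.4 (month) | Exit under section 7 (month) | Gap (days) |
|---|---|---|---|
| 1 | 3.8 | 12 | 334.8 − 84 = 251 |
| 3 | 5.8 | 12 | 273.9 − 84 = 190 |
| 6 | 8.8 | 12 | 182.6 − 84 = 99 |
| 8 | 10.8 | 12 | 121.8 − 84 = 38 |
| 9 | 11.8 | 12 | 91.3 − 84 = 7 |

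**5. Effect of a delayed restart.** If restart comes L days after progression, the 9.4 exit moves back by L and the gap becomes (12 − t) × 30.4375 − 84 − L. At month 9 this is 7.3 − L. Any delay beyond about 7 days places month 12 before the end of cycle 3, and the order of the two rules reverses. At month 3 the same formula gives 190 − L, so a delay of a week or two changes little.

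**The case against.** **Section 9 takes precedence.** Section 7 closes by referring to section 9 for details of treatment. In 9.4 the 3-cycle rule is part of the statement of how long ibrutinib is given, so a site could treat it as schedule and follow 9.4. That is a fair pointer. But the cross-reference names only dose and schedule, and section 7 states its own failure rule with its own consequence. Nothing says that the consequence is overridden.

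**The parenthesis serves only the endpoint.** Nine months plus 3 cycles is 11.76 months, so the clause may have been written to match the month-12 endpoint. Even so, its sentence ends in leaving protocol treatment, and the endpoint rules stand separately in sections 13.1 and 14.4.1.

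**Section 11.1 is compatible with both.** A reader might infer that 11.1 is a second fixed 3-cycle rule. It is not, since withdrawal at month 12 also comes after at least 3 cycles in most cases. What remains is that 11.1 is already met at cycle 3 and has no exception.

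**Few patients are involved.** This stands. They must be MRD negative in blood and marrow at randomization, progress clinically within 9 months despite MRD monitoring that can trigger an earlier restart, and then have PD on restarted treatment. A reader might infer that early relapse in general is handled inconsistently, but patients who reach SD or better by cycle 3 are not affected. The protocol gives no basis for estimating the number. Section 11.1 also lets the investigator withdraw a patient for other reasons, so section 7 need not keep every such patient on treatment to month 12.

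**The endpoint effect is not established.** This also stands. The protocol names time to treatment failure after restart without defining its event, which may properly be left to the analysis plan. If the event is documented PD, the date of leaving treatment need not move it. All analyses other than the primary are hypothesis-generating (section 14.4.6).

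**Conclusion.** The contradiction holds as protocol wording. For clinical progression within 9 months of randomization followed by PD on restarted treatment, sections 7 and 9.4 give different times for leaving protocol treatment. Section 11.1 does not support the later one, and no passage settles the matter.

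With restart on the day of progression, the times differ by about 190 days for progression at month 3 and 99 days at month 6. The difference falls to about 7 days at month 9 and can change sign if restart is delayed.

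A reader might go further and quote an average of several months of extra treatment. That would need a distribution of progression times and restart delays that the protocol does not give. A reader might also infer that the treatment-failure endpoint is certain to shift. It may, but only if leaving treatment for failure is its event. The sample size of 62 with a threshold of 44 does not depend on this point.

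**What to change.** Reconcile sections 7, 9.4 and 11.1 into one rule, worded identically in all three, for when an arm B patient without a response leaves restarted treatment. State whether any exception for early progression exists and, if so, whether it covers restarts for MRD positivity. Keep the rule consistent with the response windows in section 13.1 (up to 12 months after randomization) and section 14.4.1 (3 months from restart), which need to agree with each other as well. When the event for time to treatment failure after restart is defined, say whether it is tied to this rule. Which window applies is for the sponsor to decide.

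The cost is protocol wording and a note to sites. No patients, visits or assessments are added, and the sample size does not change.
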